7.6.5 Month 1 Visit

The following evaluations and assessments will be performed at this visit:

- Medication review (see Appendix A)
- Physical exam
- Neurological exam
- Functional assessment (including employment status, education, living arrangements, driving status)
- Seizure diary collection and dispensing (see Appendix B)
- Adverse event monitoring

7.6.6 Month 2 Telephone Call

The following assessments will be completed during this call:

- Medication review (see Appendix A)
- Seizure diary collection (see Appendix B)
- Adverse event monitoring

7.6.7 Month 3 Visit

The following evaluations and assessments will be performed at this visit:

- Medication review (see Appendix A)
- Neurological exam
- Neuropsychological testing (see Appendix C).
- Functional assessment (including employment status, education, living arrangements, driving status)
- Seizure classification update assessment
- Seizure diary collection and dispensing (see Appendix B)
- Adverse event monitoring
- Surgical outcome classifications (Engel and ILAE, see Appendix D)

7.6.8 Month 4 Telephone Call

The following assessments will be completed during this call:

- Medication review (see Appendix A)
- Seizure diary collection (see Appendix B)
- Adverse event monitoring

7.6.9 Month 5 Telephone Call

The following assessments will be completed during this call:

- Medication review (see Appendix A)
- Seizure diary collection (see Appendix B)
- Adverse event monitoring

7.6.10 Month 6 Visit

The following evaluations and assessments will be performed at this visit:

- QOLIE-31. It is preferred that the subject completes the questionnaire prior to any other tests.
- Medication review (see Appendix A)
- Physical exam
- Neurological exam
- Visual field testing (automated perimetry)
- Neuropsychological testing (see Appendix C).
- Functional assessment (including employment status, education, living arrangements, driving status)
- Seizure classification update assessment

- Seizure diary collection and dispensing (see Appendix B)
- Adverse event monitoring
- MRI
- Surgical outcome classifications (Engel and ILAE, see Appendix D)
- Subject satisfaction

7.6.11 Month 7 Telephone Call

The following assessments will be completed during this call:

- Medication review (see Appendix A)
- Seizure diary collection (see Appendix B)
- Adverse event monitoring

7.6.12 Month 8 Telephone Call

The following assessments will be completed during this call:

- Medication review (see Appendix A)
- Seizure diary collection (see Appendix B)
- Adverse event monitoring

7.6.13 Month 9 Visit

The following evaluations and assessments will be performed at this visit:

- Medication review (see Appendix A)
- Neurological exam
- Functional assessment (including employment status, education, living arrangements, driving status)
- Seizure diary collection and dispensing (see Appendix B)
- Adverse event monitoring
- Surgical outcome classifications (Engel and ILAE, see Appendix D)

7.6.14 Month 10 Telephone Call

The following assessments will be completed during this call:

- Medication review (see Appendix A)
- Seizure diary collection (see Appendix B)
- Adverse event monitoring

7.6.15 Month 11 Telephone Call

The following assessments will be completed during this call:

- Medication review (see Appendix A)
- Seizure diary collection (see Appendix B)
- Adverse event monitoring

7.6.16 Month 12 Visit

The following evaluations and assessments will be performed at this visit:

- QOLIE-31. It is preferred that the subject completes the questionnaire prior to any other tests.
- Medication review (see Appendix A)
- Physical exam
- Neurological exam
- Neuropsychological testing (see Appendix C)
- Functional assessment (including employment status, education, living arrangements, driving status)
- Seizure classification update assessment
- Seizure diary collection and dispensing (see Appendix B)
- Adverse event monitoring
- Surgical outcome classifications (Engel and ILAE, see Appendix D)
- Subject satisfaction

7.6.17 Telephone Calls (Months 13-17, 19-23)

During these phone calls the following assessments will be completed:

- Medication review (see Appendix A)
- Seizure diary collection and dispensing (see Appendix B)
- Adverse event monitoring

7.6.18 Month 18 Visit

The following evaluations and assessments will be performed at this visit:

- QOLIE-31. It is preferred that the subject completes the questionnaire prior to any other tests.
- Medication review (see Appendix A)
- Neurological exam
- Functional assessment (including employment status, education, living arrangements, driving status)
- Seizure diary collection and dispensing (see Appendix B)
- Surgical outcome classifications (Engel and ILAE, see Appendix D)
- Adverse event monitoring
- Subject satisfaction

7.6.19 Month 24 Visit

The following evaluations and assessments will be performed at this visit:

- QOLIE-31. It is preferred that the subject complete the questionnaire prior to any other tests.
- Medication review (see Appendix A)
- Neurological exam
- Functional assessment (including employment status, education, living arrangements, driving status)
- Seizure diary collection (see Appendix B)
- Adverse event monitoring

- Surgical outcome classifications (Engel and ILAE, see Appendix D)
- Subject satisfaction

7.6.20 Unscheduled Visit

Evaluations or assessments completed during an unscheduled visit will be recorded on the applicable CRFs.

7.7 Additional LITT Procedure(s)

If a subject undergoes an additional LITT MTLE procedure for persistent seizures, the following evaluations and CRFs will be completed:

- *Neuropsychological Testing* CRF (testing must be completed prior to the procedure)
- Evaluation CRF (for an unscheduled (Discharge) visit)
- LITT Procedure CRF

7.8 Early Withdrawal/Premature Discontinuation of Subjects

Subjects may be withdrawn early from the study for a number of reasons, including:

- Subjects experiencing a failed LITT treatment attempt. A failed LITT treatment attempt is defined as stopping the procedure prior to thermal delivery. (Subjects that experience a failed treatment attempt will be followed for 1 month post-procedure for related adverse events.)
- Subject death
- Subject lost to follow-up
- Subject request for withdrawal
- Adverse events
- Investigator decision (other than an adverse event)

If a study subject is discontinued from the study early, a Study Completion CRF must be completed describing the reason for early discontinuation. The investigator should make all attempts to conduct an Early Withdrawal visit at the time of withdrawal from the study. If a subject has withdrawn consent for the study or is lost to follow-up, the completion of this visit is not imperative. In situations where study withdrawal is due to an adverse event, subjects will be followed until resolution of the adverse event or determination that the subject's condition is stable.

At the Early Withdrawal visit, the subject will undergo the following evaluations:

- QOLIE-31. It is preferred that the subject completes the questionnaire prior to any other tests.
- Neurological exam (cranial nerves (including confrontation visual field testing), motor, coordination, reflexes, gait, sensation)
- Neuropsychological testing
- Adverse event monitoring
- Subject satisfaction
- Functional assessment (including employment status, education, living arrangements, driving status)
- Surgical outcome classifications (Engel and ILAE, see Appendix D)

If a subject chooses to withdraw from the study and also withdraws consent for disclosure of future information, no further evaluation(s) should be performed and no additional data will be collected. The Sponsor may retain and continue to use any data collected prior to the withdrawal of consent.

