7.6.2 LITT Procedure

An MRI will be performed prior to surgery to determine trajectory and frame/arc settings. The LITT procedure will be performed per the IFU. Adverse events that occur during the procedure will be collected.

Postoperatively, the subject should be managed per the institution's standard of care for subjects receiving LITT. This includes monitoring of the subject's neurological status as it relates to possible intraoperative or postoperative adverse events (including intracranial hemorrhage).

Subjects experiencing a failed LITT treatment attempt (stopping the procedure prior to thermal delivery) will be followed for 1 month post-procedure for adverse events.

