10.1.1 Primary Endpoint: Analysis of Adverse Events

For adverse events, both event counts and counts of subjects experiencing those events will be reported in tabular summaries. Rates will be reported based on the number of subjects experiencing one or more event as a proportion of all enrolled subjects and these subject rates will serve as the primary analysis.

Adverse event analysis may be repeated for events that occur after the initiation of treatment with rates calculated as a proportion of treated subjects, if it occurs that not all enrolled subjects undergo treatment with LITT.

Event counts, subject counts, and subject rates will also be reported for the following subsets of adverse events: SAE, SADE, UADE, USADE. Adverse events will be further characterized by tabulating the event severity and relationship (see section 9.1).

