10.2.2 Analysis Populations

All subjects enrolled in the study (including those withdrawn from the investigation) will be accounted for and documented.

The following analysis populations are defined:

Enrolled Set: All subjects enrolled in the study

Treated Set: All subjects that initiate treatment with LITT (received thermal delivery with the NBS)

Per-protocol Set: All subjects in the Treated Set that are treated according to the protocol requirements and meet study and treatment eligibility criteria

In the feasibility study setting, conclusions about performance are best informed by analyses of the Treated Set. Analyses may be repeated on the Enrolled Set for full reporting of study results and on the Per-protocol Set to provide insight into the potential impact of protocol deviations on the analysis results.

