Up to 45 subjects will be enrolled at up to 8 sites in the United States to ensure that approximately 30 subjects undergo the LITT procedure. It is expected that each site will enroll no more than 10 subjects to ensure that all sites have an opportunity to contribute data to the study and to prevent any one site from having an outsized influence on the overall results of the study.

10 Analysis Populations

The following analysis populations are defined:

- **Enrolled Set:** All subjects enrolled in the study
- **Treated Set:** All subjects that received thermal delivery with the NBS
- **Per-protocol Set:** A subset of the Treated Set that does not have a protocol deviation (see below)

In the feasibility study setting, conclusions about performance are best informed by analyses of the Treated Set. Analyses may be repeated on the Enrolled Set for full reporting of study results and on the Per-protocol Set to provide insight into the potential impact of protocol deviations on the analysis results.

The Per-protocol Set will exclude subjects with protocol deviations that seriously affect the integrity of the data. The deviations that will result in subject data being excluded from the Per-Protocol Set are:

1. Subject did not meet the following study inclusion criteria:

- Diagnosis of unilateral medial temporal lobe epilepsy (MTLE) confirmed clinically and with either (1) ictal scalp recording and MRI evidence of mesial temporal sclerosis or (2) intracranial ictal onset consistent with hippocampal origin.
- Subject or legally authorized representative is able to provide appropriate consent to participate.
- Subject averages 3 or more complex partial seizures (with or without secondary generalization) per month over the 3 most recent consecutive months prior to baseline.

2. Subject should not have undergone the study procedure (i.e. subject was found not to have met the treatment eligibility criteria in Section 6.4 of the clinical study protocol)

Protocol deviations may be reviewed prior to performing analysis of study outcomes to identify deviations, in addition to those identified above, that may result in excluding a subject from the per-protocol set. Reviewing protocol deviations prior to analysis of outcomes is intended to prevent bias in the analysis results while still allowing for identification of significant protocol deviations that could impact outcomes but that were not anticipated at the time that the Statistical Analysis Plan was written.

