11.1.1 Primary Endpoint: Analysis of Adverse Events

Adverse events will be presented in summary tables displaying the number of events, the number of enrolled subjects with ≥ 1 event, and the proportion of enrolled subjects with ≥ 1 event. The rates of adverse events will serve as the primary analysis.

Adverse event analysis may be repeated for only those events that occur after the initiation of treatment with rates calculated as a proportion of treated subjects..

Phase

The timing of adverse events relative to the initial LITT procedure will be tabulated by reporting the event counts, subject counts, and subject rates of events that occur within the following phases:

- **Baseline:** Prior to LITT procedure
- **Operative:** From the beginning of the LITT procedure through 30 days post-procedure
- **Year 1:** From 31 days post-procedure through 12 study months (12 month visit date or close of 12 month visit window if 12 month visit is missed)
- **Year 2:** After 12 study months through 24 study months (24 month visit date or close of 24 month visit window if 24 month visit is missed)

Additional analyses may be performed that divide the above phases into more detailed time intervals or that combine phases to present an overall summary of all adverse events through a specific time point (e.g. Operative Through Year 2).

Severity

The severity of adverse events will be tabulated by reporting the event counts, subject counts, and subject rates of events that are:

- **Mild:** Does not interfere in a significant manner with the subject's normal functioning level.
- **Moderate:** Produces some impairment of functioning but is not hazardous to health.
- **Severe:** Produces significant impairment of function or incapacitation and is a hazard to the subject's health.

Relationship

The relationship of adverse events to the device treatment or procedure will be tabulated by reporting the event counts, subject counts, and subject rates of events based on the following relationship categories:

- **Definite** – The adverse event follows a strong temporal sequence to the receipt (or attempted receipt) of the device treatment or procedure. This can include an adverse event that occurs after the study procedure.

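### Protocol 7.6.2 and 7.8 disagree on which adverse events are collected after a procedure stopped before heating, and no adverse event table uses procedures started as its denominator

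*Protocol*

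**What the plan says.** **Collection after a failed attempt.** Protocol 7.8 defines a failed attempt as one stopped before thermal delivery and states: "Subjects that experience a failed treatment attempt will be followed for 1 month post-procedure for related adverse events". Protocol 7.6.2, on the same subjects, says they "will be followed for 1 month post-procedure for adverse events", with no limit to related events. Section 9.1 defines an adverse event regardless of relatedness and starts collection on the procedure day. Section 9.2 has the investigator evaluate any event from that day to the end of participation and has the site report all of them.

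**Analysis.** In protocol 10.1.1, "Rates will be reported based on the number of subjects experiencing one or more event as a proportion of all enrolled subjects", and these rates are the primary analysis. SAP 11.1.1 also uses enrolled subjects and adds that "The rates of adverse events will serve as the primary analysis". A second analysis is optional: "Adverse event analysis may be repeated for events that occur after the initiation of treatment with rates calculated as a proportion of treated subjects". The protocol makes this conditional on some enrolled subjects not being treated; the SAP drops the condition.

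**Treated Set.** SAP section 10 defines it as "All subjects that received thermal delivery with the NBS". Protocol 10.2.2 has the same criterion and equates initiating treatment with thermal delivery. Both documents say that "conclusions about performance are best informed by analyses of the Treated Set".

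**Phases.** In SAP 11.1.1 the Operative phase starts when the LITT procedure begins, not at heating.

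**The concern.** Safety is the primary endpoint, and part of the procedural risk arises before any heat is delivered. Protocol 11.1 lists bleeding in or around the brain and injury to blood vessels among the risks. Two things follow.

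First, a site cannot tell from the protocol which events to record in the month after a failed attempt. If it follows 7.8, it decides relatedness before reporting. The Clinical Events Committee is one of the protocol's stated bias controls (section 8), and under SAP 15.3 its category replaces the investigator's where available. It cannot reclassify an event it never receives.

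Second, a complication during access or probe placement may itself be the reason heating never starts. A safety table restricted to heated subjects then excludes subjects partly because of their outcome, and so leans towards uncomplicated placements.

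**Working it through.** **Step 1: the collection rules side by side.**
- 7.6.2: one month, adverse events.
- 7.8: one month, related adverse events only.
- 9.1 and 9.2: all adverse events, related or not, from the procedure day to the end of participation.

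These cannot all be followed. The events at risk are those the site judges unrelated after a failed attempt.

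**Step 2: where a placement complication is counted.**
- Case stopped before heating: counted in the enrolled-set analysis, numerator and denominator. The subject is outside the Treated Set, so is in neither part of the treated-subject repeat.
- Event before heating, subject then heated: counted in the enrolled-set analysis. In the repeat the subject is in the denominator, but on the wording of protocol 10.2.2 the event precedes initiation of treatment and is not in the numerator.
- Enrolled but never operated on: SAP 12.2 expects to count such exits. They are in the enrolled denominator only.

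No table has all procedures started, and only those, as its denominator.

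**Step 3: the plan's own figure.** Both documents give about an 80% chance of seeing at least one event of 5% per-subject probability in 30 subjects: 1 − 0.95^30 = 0.785. This reproduces and is not affected by the present point.

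**Step 4: illustration.** The documents give neither a failed-attempt count nor a rate of access harm, so every count below is assumed. Intervals are exact 95% (Clopper-Pearson, the method named in SAP 12.1): lower limit = Beta quantile(0.025; x, n − x + 1), upper limit = Beta quantile(0.975; x + 1, n − x), with lower limit 0 when x = 0. Each row has 30 heated subjects. The last column assumes enrolment at the SAP's ceiling of 45. The SAP was written for protocol Rev A, and that ceiling is not in the Rev B protocol.

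| Assumed harms | Treated-subject repeat | Procedures started | Enrolled, if 45 |
|---|---|---|---|
| 1 after heating; 2 attempts stopped by a harm | 1/30 = 3.3% (0.1–17.2) | 3/32 = 9.4% (2.0–25.0) | 3/45 = 6.7% |
| 0 after heating; 2 attempts stopped by a harm | 0/30 = 0% (0–11.6) | 2/32 = 6.25% (0.8–20.8) | 2/45 = 4.4% |
| 2 after heating; 3 attempts stopped by a harm | 2/30 = 6.7% (0.8–22.1) | 5/33 = 15.2% (5.1–31.9) | 5/45 = 11.1% |
| 2 after heating; 1 uneventful failed attempt | 2/30 = 6.7% (0.8–22.1) | 2/31 = 6.5% (0.8–21.4) | 2/45 = 4.4% |
| 1 before heating in a subject then heated; no failed attempt | 0/30 = 0% (0–11.6) | 1/30 = 3.3% (0.1–17.2) | 1/45 = 2.2% |

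The fourth row shows that an uneventful failed attempt moves the rate slightly the other way. If everyone enrolled were operated on, the enrolled and procedures-started columns would be equal (3/32 = 9.4% in the first row).

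**The case against.** A reader might infer that harms of drilling and probe placement are under-counted in this trial's safety results. The documents do not support that.
- The primary adverse event analysis in both documents is on enrolled subjects. A failed-attempt subject is enrolled, so a reported insertion bleed stays in it.
- The table that loses such events is an optional repeat alongside the primary one.
- Protocol 9.1 judges relatedness to the device treatment or the procedure, and four of its five categories include attempted receipt. A placement harm would ordinarily be judged related and so be collected even under 7.8.
- Section 7.6.2 separately collects events during the procedure, and the Early Withdrawal visit in 7.8 includes adverse event monitoring without a relatedness limit.
- The preference for the Treated Set concerns conclusions about performance. The objective uses that word broadly enough that safety may be included, but the specific rule for adverse events names enrolled subjects.
- It would also be too strong to say that the committee alone decides relatedness. The investigator assesses it, and the committee's category is used where available.

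All of this stands, and it confines the point. It does not settle which events are collected under 7.8, and it does not supply a rate per procedure started. The relatedness argument is also a little weaker in the SAP, where the definitions of Possible and Unlikely omit attempted receipt.

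**Conclusion.** The point holds in a limited form. Sections 7.6.2 and 7.8 contradict each other, and 7.8 also conflicts with 9.1 and 9.2. What may be lost is any event after a failed attempt that the site judges unrelated. Separately, the optional treated-subject table excludes placement complications that stop the case and, if initiation of treatment means thermal delivery as protocol 10.2.2 indicates, also events before heating in subjects later heated. The primary table retains all of these once reported, possibly over a diluted denominator.

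The size cannot be stated from the documents. With 30 heated subjects and two attempts assumed to be stopped by a harm, the gap is about 6 percentage points (3.3% against 9.4%), with wide and overlapping intervals. It is zero if no attempt fails and no event precedes heating. With about 30 subjects and purely descriptive reporting, one or two events visibly change the rate. The correction is worth making, but the primary safety analysis is not invalid without it.

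**What to change.** 1. **Protocol 7.8:** remove the word *related*, so that 7.8 agrees with 7.6.2, 9.1 and 9.2. All adverse events in the existing one-month period are then recorded and available for adjudication. The length of follow-up does not change.
2. **Protocol 10.1.1 and 10.2.2, SAP 10 and 11.1.1:** keep the enrolled-set analysis as primary. Define one further set, all subjects in whom the LITT procedure began, whether or not heat was delivered. Run the treated-subject adverse event repeat on that set, counting events from the start of the procedure, as the SAP's Operative phase already does. Omit failed-attempt subjects from the Year 1 and Year 2 rows, since their follow-up ends at one month.

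The Treated Set can stay as it is for seizure and quality-of-life outcomes.

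Cost: one deleted word and one set definition in each document, with no new visits. The reported procedural adverse event rate may be slightly less favourable than in a table limited to heated subjects.

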2 INTRODUCTION

Since its introduction to neurosurgery over 25 years ago, laser ablation had been largely confined to the management of unresectable tumors. The application of this technology for management of medically refractory epilepsy is being explored as a treatment option.^{1, 2} Laser interstitial thermal therapy (LITT) is a minimally invasive option to open surgical intervention that necrotizes abnormal intracranial tissues. LITT's use in neurosurgical procedures was historically limited by early technical difficulties related to the monitoring and control of thermal distribution. The development of magnetic resonance thermography and its application to LITT provides real-time thermal imaging and feedback control during laser energy delivery, resulting in precise and accurate delivery of tissue hyperthermia. Improvements in laser probe design, surgical stereotactic targeting hardware and computer monitoring software has accelerated clinical utilization of LITT as a refractory epilepsy treatment alternative for eligible patients although clinical outcome data is limited.¹

The NeuroBlate® System (NBS) is a robotic laser thermotherapy tool manufactured by Monteris Medical (Sponsor). The NBS combines magnetic resonance imaging (MRI) and software-based visualization allowing the surgeon to necrotize targeted tissues at the surface of or deep inside the brain through a pencil-sized hole in the skull. An MRI compatible robotic probe driver helps the surgeon precisely guide the laser probe to the targeted tissue and apply heat to it in controlled amounts under guidance of real-time MR thermography, until the tissue is destroyed.

The Sponsor designed this multicenter, open-label, prospective feasibility study to characterize the performance of LITT ablation using the Monteris NBS for the treatment of drug refractory medial temporal lobe epilepsy in subjects who are candidates for surgical resection.

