9.2 Reporting

Subjects will be carefully monitored during the study for possible AEs. Any AE that occurs between the day of the procedure and the end of study participation will be fully evaluated by the investigator.

The Site will report all AEs (anticipated and unanticipated) on an *Adverse Event CRF*. Copies of source documentation which contain significant information related to the event such as progress notes, consultations, nurse's notes, operative reports and subject summaries, etc. may be requested by the

Sponsor or CRO as needed for evaluation of SAEs and ADEs. Copies of such documentation will be obtained from the investigator (or authorized delegate), de-identified as to the subject's identity, and provided to the Sponsor or CRO.

Device malfunctions will be recorded on the LITT Procedure and Discharge CRF. If a device malfunction results in the subject experiencing any untoward medical occurrence, unintended disease or injury, or untoward clinical signs, it will also be reported as an adverse event on an *Adverse Event CRF*.

In case of subject death, it is requested that a copy of the death certificate and a copy of the autopsy report, if applicable, be sent to the Sponsor or CRO when available. Any other source documents related to the death should also be provided to the Sponsor or CRO. In the event that no source documents are available, the PI is required to describe the circumstances of the subject's death in a letter, e-mail or other written communication.

USADEs have special reporting requirements for both the investigator and Sponsor, as described in 21 CFR 812.150:

- Investigator Report: If a subject experiences an USADE, the investigator must notify Monteris and the reviewing IRB as soon as possible, but in no event later than 10 working days after the investigator first learns of the effect.
- Sponsor Report: USADEs will be reported to Food and Drug Administration (FDA), all reviewing IRBs, and participating investigators as soon as possible, but no later than 10 working days, after receiving notice of the USADE(s).

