12.7 Time Point of Interest

The study was designed to follow subjects through 24 months post-procedure and 24 months has been identified as a time point of primary interest. Analyses will be performed to assess the consistency of study endpoints over the 24 month time period and the degree of predictability of later outcomes based on outcomes observed at earlier time points (e.g. correlation between seizure rate for the time period of 6 to 12 months and seizure rate for the time period of 12 to 24 months).

13 Subgroup Analyses

Descriptive subgroup analyses for each endpoint will be performed to characterize the consistency of overall study estimates across the following pre-specified groups:

1. Age (tertiles of age)
2. Race (white vs non-white)
3. Gender (male vs female)
4. Baseline seizure frequency (tertiles of baseline seizure frequency)

5. Time since epilepsy diagnosis (tertiles of years since diagnosis)
6. Prior/concurrent VNS treatment (yes vs no)

Subgroup results will only be reported for subgroups that have at least 5 subjects since the smaller the sample size in a subgroup, the less likely it is that the observed results will be generalizable to the subgroup population.

Additional ad hoc subgroup analyses may be performed after all subjects have been enrolled, depending on the subject demographics and available sample size.

14 Treatment Factors Analyses

Descriptive analyses for each endpoint will be performed to characterize the potential relationship between treatment factors and study endpoints.

Treatment factors that will be analyzed include:

1. Complete versus incomplete LITT procedure
2. Abnormal findings on post-op images (e.g. edema, hemorrhage, infarction, or collateral damage)
3. Trajectory anatomic measurements
4. Ablation volume

15 Data Handling

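### Protocol 7.8 lets an adverse event end study follow-up after thermal delivery, so new adverse events and later assessments in those subjects go uncollected

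*Protocol*

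**What the plan says.** Protocol 7.8 opens its list with "Subjects may be withdrawn early from the study for a number of reasons, including". The list contains a failed treatment attempt, death, loss to follow-up, subject request, adverse events, and investigator decision for a reason other than an AE. No criteria are given for the last two, and neither is confined to subjects without thermal delivery.

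On what follows an AE withdrawal, the section says: "In situations where study withdrawal is due to an adverse event, subjects will be followed until resolution of the adverse event", or until the condition is judged stable. The section also asks for an exit assessment: "The investigator should make all attempts to conduct an Early Withdrawal visit at the time of withdrawal from the study". That visit includes QOLIE-31, neurological examination, neuropsychological testing, AE monitoring and Engel/ILAE class.

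Protocol 9.2 sets the collection period: "Any AE that occurs between the day of the procedure and the end of study participation will be fully evaluated by the investigator". SAP 12.7 states that "24 months has been identified as a time point of primary interest".

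On the treatment, Protocol section 2 says: "Laser interstitial thermal therapy (LITT) is a minimally invasive option to open surgical intervention that necrotizes abnormal intracranial tissues". Neither document describes a study therapy that continues after the procedure.

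**The concern.** Withdrawal because of an AE makes sense where a therapy can be stopped. After ablation what remains of the study is observation: office visits, telephone calls, diary, questionnaires and testing. Withdrawing a treated subject because of an AE removes no exposure and ends only data collection.

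Safety is the primary endpoint, follow-up is planned to 24 months and about 30 subjects are to be treated. Subjects who leave after an AE may differ from those who stay in later AEs, seizure outcome and quality of life. If they do, the later results describe a selected group, and with 30 subjects two or three exits can move a percentage noticeably.

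**Working it through.** **1. The plan's own figure.** Protocol 10.2.4 and SAP section 9 give 30 subjects, a 5% per-subject AE probability and about an 80% chance of seeing at least one case. Check: 1 − 0.95^30 = 1 − 0.2146 = 78.5%. The figure reproduces. It takes all 30 as fully observed.

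**2. Non-selective loss barely moves that figure.** No withdrawal rate is given, so the losses here are assumed.
- Milder case: the 5% risk is spread evenly over 24 months and k subjects leave at Month 6. Their observed risk is 0.05 × 6/24 = 0.0125, and the chance is 1 − 0.95^(30−k) × 0.9875^k. Results: k = 1, 77.7%; k = 3, 75.9%; k = 6, 72.9%.
- Worst case: those who leave count as never observed, so the chance is 1 − 0.95^n. Results: n = 28, 76.2%; n = 27, 75.0%; n = 24, 70.8%; n = 21, 65.9%.

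Detection of a 5% event is therefore not the main issue. Selective loss is.

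**3. What happens to each outcome after an AE withdrawal.**
- *Triggering AE:* kept. Protocol 10.1.1 and SAP 11.1.1 use all enrolled subjects as denominator, and the event is followed to resolution or stability.
- *New AEs:* not collected once participation ends (Protocol 9.2). SAP 11.1.1 also tabulates subject rates by phase, including Year 1 and Year 2. The phase paragraph names no denominator of its own. On the enrolled denominator that opens the section, a withdrawn subject adds 1 below the line and nothing above it, and so counts as event-free in later phases. This can only lower those rates.
- *Cognition:* the core battery is scheduled at Early Withdrawal in both languages (Protocol Appendix C, Tables 5 and 6). The supplementary battery is not. SAP 15.2 assigns data to the time point on the CRF, and no rule places an exit test at Month 12. Appendix C itself explains that outcome is usually assessed at 6 to 12 months because most recovery has occurred by then, so an early exit test is not equivalent.
- *Engel/ILAE:* tabulated at each visit among subjects completing that visit (Protocol 10.1.3, SAP 11.1.3). Withdrawn subjects drop out of later tables.
- *Seizure frequency:* the main analysis requires 70 diary days per 3 months to Month 12 and 140 per 6 months thereafter to study completion. Read literally, a subject withdrawn early in Year 2 is left out even with a complete first year.
- *Freedom from seizures:* the Kaplan-Meier analysis censors at the last completed diary date (SAP 11.1.3), which is informative if exit is related to prognosis.
- *QOLIE-31:* the 24-month estimate is of primary interest (Protocol 10.1.4); an exit questionnaire is not a Month 24 value.

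**4. Illustration for a completers-only table (assumed counts).** Let b of 30 have a poor outcome and let m of those b leave. The observed proportion is (b − m)/(30 − m).
- b = 6: 6/30 = 20.0% with no exits; 5/29 = 17.2% with one; 4/28 = 14.3% with two; 3/27 = 11.1% with three.
- b = 3: 3/30 = 10.0% becomes 1/28 = 3.6% with two exits.
- Opposite direction: if two subjects with a good outcome leave instead, 6/28 = 21.4%; if three, 6/27 = 22.2%.

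The direction in such tables depends on who leaves.

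**The case against.** The case against is substantial on several points.

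- A reader might infer that harmed subjects vanish from the safety data. The documents do not support that. The AE behind the withdrawal stays in the primary rate, is followed up, and SAP section 17 keeps all available dropout data.
- A reader might take cognition as lost. The exit battery covers the core tests, and no cognitive test is scheduled after Month 12 for those who stay, so the 24-month argument does not apply to it. The gap is the Month 12 battery in subjects who leave before then.
- Investigator decision is expressly for reasons other than an AE. Nothing says it is used for subjects who are doing badly.
- LITT is not strictly a single procedure, since Protocol 7.7 foresees repeats. A repeat still leaves no continuing therapy to stop.
- The list is permissive and partly reads as disposition categories. Protocol 7.9 asks for every attempt to have subjects complete the schedule.
- Withdrawals are tabulated by reason, and SAP section 17 describes worst-case imputation.

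All of this narrows the point. It does not remove it. The general aim in 7.9 sits beside a section that lets the investigator end the schedule because of an AE. The missing-data analyses in Protocol 10.2.3 and SAP section 17 only may be performed, and no imputation recovers AEs that were never asked about.

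**Conclusion.** The point holds in limited form. Section 7.8 permits AE withdrawal of thermally treated subjects and requires no follow-up to Month 24 afterwards. What is lost is new AEs, the Month 12 core battery if exit is earlier, and diary, Engel/ILAE class and QOLIE-31 to Month 24. Missing later AEs can only lower the later-phase rates if the enrolled denominator applies; for the other outcomes the direction is not established.

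The size cannot be computed, because the documents give no withdrawal rate. The fall from 20.0% to 14.3% or 11.1% rests on assumed counts in which only subjects with poor outcomes leave. It applies to a completers-only table such as Engel/ILAE and should not be read as an expected bias, nor applied to cognition without allowing for the exit battery. The study is descriptive with no hypothesis tests, so no test result is at risk. This is an inexpensive improvement to retention, not a flaw that invalidates the primary AE analysis.

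**What to change.** In Protocol 7.8:

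1. State that, for subjects who received thermal delivery, an adverse event is not in itself a reason to end study follow-up. They continue the scheduled visits and calls to Month 24 unless they withdraw consent, die or are lost to follow-up. Where visits are not feasible, AEs, diary and medication are collected by telephone.
2. For a withdrawal by investigator decision, continue at least AE and seizure-outcome collection by telephone, with the subject's consent.
3. Keep the current list for subjects without thermal delivery, a distinction that 7.8 already draws.

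The cost is a short edit and a few more visits or calls, all already in the schedule, in subjects who may be harder to follow. The change concerns observation only and leaves the right to withdraw consent intact. Its limit is that telephone contact does not replace the Month 12 cognitive battery, so some cognitive data may still be missing.
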